# 8.6 Suspected Unexpected Serious Adverse Reactions (SUSARs)

SUSARs refer suspected unexpected serious ADRs whose clinical manifestations are beyond the Investigator's Brochure for the investigational drug, package inserts for marketed drugs, summary of product characteristics and other existing information in terms of their nature and severity.

After receiving safety-related information from any source, the sponsor should immediately analyze and assess, including the severity, causality with the investigational drug, and whether it is an expected event. The sponsor should report SUSARs to all participating investigators, clinical trial institutions and Ethics Committees in an expedited manner; the sponsor should report SUSARs to drug regulatory authorities and health authorities.

After receiving the relevant safety information of the clinical trial provided by the sponsor, the investigator should sign and read it in time, and consider whether to make corresponding adjustments to the treatment of the subject. If necessary, the investigator should communicate with the subject as soon as possible, and report SUSAR provided by the sponsor to the Ethics Committee.

In addition, the sponsor should make an expedited reporting of SUSARs to the center for drug evaluation (CDE) in a manner of individual case safety report (ICSR)according to *Criteria and Procedures for Expedited Reporting of Safety Data During Drug Clinical Trial* Issued by CDE on April 2018. For SUSARs, if the sponsor and the investigator can't agree on the causal relationship between the AE and the drug and any party considers that it is unable to exclude the correlation, expedited reporting should also be carried out.

#### The time limit for expedited reporting of SUSARs:

- (I) For fatal or life-threatening SUSARs, the sponsor should report them as soon as possible and not more than 7 days after the first awareness, and should report and improve the follow-up information within the next 8 days. Note: The day of the sponsor's first awareness is Day 0.
- (II) For non-fatal or life-threatening SUSARs, the sponsor should report them as soon as possible and not more than 15 days after the first awareness of the event.

After the initial report, the sponsor should continue following up the event and report relevant new information or update the previous report in the form of follow-up report timely (within 15 days after obtaining the new information).

#### 8.7 Pregnancy

Pregnancy itself is not an AE or SAE. However, if the outcome of the pregnancy meets SAE criteria (e.g., spontaneous abortion, stillbirth, death neonatal, congenital anomaly or birth defect), the

corresponding event should be reported as an SAE.

For the contraceptive measures, definitions of child-bearing potential women, and contraceptive requirements, see Appendix III.

# Female subjects become pregnant:

If female subjects are found pregnant during the study (from the start of administration to within 3 months after the last dose), the investigator should complete Pregnancy Reporting Form within 24 hours of awareness, report to the sponsor/CRO in an expedited manner, record it in the source medical records and the eCRF, and follow up the outcome of pregnancy (e.g., normal birth, preterm labour, spontaneous abortion, induced abortion, death neonatal, congenital anomaly or birth defect, etc.).

The investigator should propose advice to the subjects and discuss the risks of continuing pregnancy and the possible effects on the fetus. The subjects should terminate the study drug and withdraw from the study, and they should be monitored continuously until the end of pregnancy.

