Single-dose and 7-day repeat-dose PK studies in Beagle Dogs: Following intravenous and oral administration of BB102-citrate in Beagle dog, the AUClast ratio between males and females was 1.00-1.34, and the  $C_{max}$  ratio between males and females was 0.983-1.38, indicating that there was no obvious gender difference for the exposure. Following intravenous administration of BB102citrate at 1 mg/kg in Beagle dogs, the AUClast of BB102 in Beagle dogs was 2040 h\*ng/mL; BB102 was a low clearance compound in Beagle dog, and it was extensively distributed in Beagle dogs. Following single oral administration of BB102-citrate at three dose levels (i.e., 10 mg/kg, 30 mg/kg and 90 mg/kg) in Beagle dog, the AUClast were 14562 h\*ng/mL, 27598 h\*ng/mL and 27415 h\*ng/mL, respectively; the Cmax were 4492 ng/mL, 8687 ng/mL and 8292 ng/mL, respectively; the  $T_{1/2}$  were 6.54 h, 6.30 h and 7.26 h, respectively. The increase of  $C_{max}$  and  $AUC_{last}$  were slightly lower than dose-proportional in the dose range of 10-30 mg/kg; however, Cmax and AUClast did not increase in the dose range of 30-90 mg/kg. It was speculated that there might be saturated absorption in the animals (Beagle dogs) in the dose range of 30-90 mg/kg. Following 7-day repeat oral administration of BB102-citrate at 30 mg/kg, the Cmax and AUClast ratios between Day 7 and Day 1 in Beagle dog were 1.07 and 1.22, respectively, indicating there was no obvious accumulation of BB102 in Beagle dog following 7-day repeat-dose at 30 mg/kg. When it was calculated using AUClast, following single oral administration of BB102-citrate at 10 mg/kg in Beagle dog, the absolute bioavailability in Beagle dog was 71.1%.

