(3) For the dose escalation trial, at least one evaluable tumor lesion according to the Response Evaluation Criteria in Solid Tumors (RECIST) v1.1 (Appendix I).

For the expansion trial, at least one measurable tumor lesion according to RECIST v1.1.

- (4) Eastern Cooperative Oncology Group (ECOG) performance status score of ≤1 (Appendix II).
- (5) Life expectancy of  $\geq 3$  months.
- (6) With good organ function, including:

Liver function: TBIL  $\le$ 1.5 × upper limit of normal (ULN), ALT  $\le$ 3×ULN, and AST  $\le$ 3×ULN (for patients with liver cancer or liver metastases, the criteria will be TBIL  $\le$ 3×ULN, ALT  $\le$ 5×ULN, and AST  $\le$ 5×ULN);

- ➤ Renal function: blood creatinine ≤1.5×ULN and creatinine clearance rate ≥50 mL/min (calculated based on Cockcroft-Gault formula);
- Hematology (no blood transfusion or hematopoietic stimulating factor therapy within 14 days of blood sampling for hematology): blood platelet (PLT)  $\geq 100 \times 10^9$ /L (for patients with liver cancer, the criteria will be PLT  $\geq 85 \times 10^9$ /L), absolute neutrophil count (ANC)  $\geq 1.5 \times 10^9$ /L, and Hb  $\geq 90$  g/L (90 mg/mL);
- ➤ Coagulation function: activated partial thromboplastin time ≤1.5×ULN and international normalized ratio ≤1.5×ULN.
- (7) For female patients of childbearing potential, the pregnancy test result within 7 days before the first dose is negative and promise to use adequate and effective methods of contraception or abstinence from the start of screening period to 6 months after the last dose of study treatment; male patients who promise to use adequate and effective methods of contraception or abstinence from the start of screening period to 6 months after the last dose of study treatment. The definition of female with childbearing potential and contraceptive requirements are detailed in Appendix III.
- (8) Voluntarily participate in this clinical study, understand the content of the ICF and sign it voluntarily, with good compliance.

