### Female partners of male subjects become pregnant:

If the female partners of male subjects are found pregnant during the study (from the start of administration to within 3 months after the last dose), the investigator should complete Pregnancy Reporting Form within 24 hours of awareness, report to the sponsor/CRO in an expedited manner, record it in the source medical records and the eCRF. Under the permission of the study site, the pregnant partner should sign an authorization form of the use and release of pregnancy health information to allow the follow-up for the outcomes of their pregnancy (e.g., normal birth, preterm labour, spontaneous abortion, induced abortion, stillbirth, death neonatal, congenital anomaly or birth defect, etc.).

The investigator should propose advice to the subjects and their female partners and discuss the risks of continuing pregnancy and the possible effects on the fetus. The male subjects are not required to discontinue the study drug or withdraw from this study, however, their female partners should be monitored until the end of pregnancy.

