# Males of reproductive potential and females of childbearing potential must also agree to one of the following from the time of signing the ICF through the last dose of study drug:

- Total abstinence. Periodic abstinence methods (such as calendar method, ovulation method, symptom-body temperature method, post-ovulation method) are not allowed.
- One of the contraceptive methods with a failure rate of <1%:
  - Intrauterine device or intrauterine hormone release system with an annual failure rate of <1%;

  - Males undergo vasoligation;
  - Double barrier method: Condoms and/or occlusion caps (diaphragm or cervical cap/dome cap), spermicide (foam/gel/film/cream/suppository) barrier method should be used as supplementary measures

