# Within 6 months after the last administration, you can also accept the following contraceptive methods:

• Reasonable combined use of oral/injection/transdermal hormonal contraceptives that can

inhibit ovulation (including estrogen and progesterone);

• Reasonable use of progesterone-only oral/injection/transdermal hormonal contraceptives that can inhibit ovulation.

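### Pregnancy reporting stops 3 months after the last dose, although contraception is required for 6 months

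*Protocol*

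**What the plan says.** Three parts of the protocol bear on this.

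- **Reporting (section 8.7).** The paragraph on female subjects begins "If female subjects are found pregnant during the study (from the start of administration to within 3 months after the last dose". If that condition is met, the investigator must submit the Pregnancy Reporting Form within 24 hours, report expeditiously to the sponsor or CRO, make an eCRF entry and follow the pregnancy to its outcome. The paragraph on male subjects applies the form, the report and the eCRF entry to partners who "are found pregnant during the study (from the start of administration to within 3 months after the last dose". Outcome follow-up there depends on site permission and the partner's authorization. Section 8.7 also states "Pregnancy itself is not an AE or SAE", but requires an SAE report "if the outcome of the pregnancy meets SAE criteria".
- **Contraception (section 3.1, criterion 7, repeated in the synopsis).** Women of childbearing potential and men must use contraception or abstain "from the start of screening period to 6 months after the last dose of study treatment".
- **Appendix III.** Subjects "must also agree to one of the following from the time of signing the ICF through the last dose of study drug". A second list then opens with "Within 6 months after the last administration, you can also accept the following contraceptive methods" and adds hormonal methods.

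Nothing in the protocol explains why the reporting period is shorter than the contraception period.

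**The concern.** The sponsor chose 6 months as the time after dosing in which conception should be avoided. A pregnancy in that time means the precaution failed, and such pregnancies should be documented and followed. Section 8.7 stops asking halfway through.

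Its trigger is also the date on which the pregnancy is found, not the date of conception. A pregnancy conceived inside the first 3 months but recognized after them falls outside the rule too.

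This is first-in-human work: section 1.6 states that there are no clinical data yet. Pregnancies identified and followed before the outcome is known give the least biased information on exposed pregnancies. If only bad outcomes come to light, there is no count of normal ones to set against them.

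**Working it through.** No sample size or error rate is involved. The check compares two periods and looks for another rule that closes the gap.

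**Step 1. The gap from the documents alone.** Contraception lasts 6 months after the last dose (criterion 7). The reporting window lasts 3 months (section 8.7). The difference is 6 − 3 = 3 months, half of the post-dose contraception period.

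**Step 2. Effect of a detection-based trigger.** Let L be the time in months from conception to detection. The protocol gives no value, so L = 0.5, 1 and 2 are assumed. A conception at month c after the last dose is covered now only if c + L ≤ 3. The uncovered part of the 6 months is then 6 − (3 − L) = 3 + L.

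| Rule | Uncovered, L = 0.5 | L = 1 | L = 2 |
|---|---|---|---|
| Found within 3 months (present) | 3.5 | 4 | 5 |
| Found within 6 months | 0.5 | 1 | 2 |
| Conceived within 6 months, whenever known | 0 | 0 | 0 |

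These are calendar months, not risks. Replacing 3 by 6 and leaving the trigger on detection would still miss L months.

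**Step 3. Other rules that might capture the pregnancy.**

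- Routine AE collection ends 28 days after the last dose, or earlier if new anti-tumor therapy starts (section 8.1.2). Drug-related AEs are still recorded later, but pregnancy itself is not an AE.
- Section 8.7 makes spontaneous abortion, stillbirth, neonatal death and congenital anomaly SAEs, with no 3-month limit. Section 8.3.1 also lists birth defects, including those suspected to come from a parent's exposure.
- So adverse outcomes are covered if the investigator learns of them. The pregnancy itself, a normal outcome and follow-up before the outcome is known are not.

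**Step 4. Drug exposure in late conceptions.** The longest oral half-life in the rat and dog PK studies (section 1.5.2) is the last of the dog values, which "were 6.54 h, 6.30 h and 7.26 h, respectively". Five half-lives are 5 × 7.26 = 36.3 h, about 1.5 days. If the human half-life were ten times longer (an assumption), this would be 363 h, about 15.1 days. The human value is unknown.

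**Step 5. Data cutoff.** Section 4.7 sets the cutoff 8 weeks after the last subject starts treatment. If that subject's first and last dose fall in week 0, 3 months ends at week 13 (13 − 8 = 5 weeks after cutoff) and 6 months at week 26 (26 − 8 = 18 weeks after cutoff). The present rule already runs past the cutoff.

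**The case against.** The strongest reply is that the two periods serve different purposes. Criterion 7 is a promise made at entry and section 8.7 is a reporting duty. A site can comply with both, and no text says they must be equal. That is right: this is a poorly matched pair of rules, not a contradiction that makes the trial unworkable.

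The exposure argument also has force. About 15 days (0.5 month) for five half-lives in the pessimistic case, plus 2 months to detection, is about 2.5 months, inside the present window. On those assumptions the current rule catches every pregnancy conceived while drug is still present. But the tenfold factor and the detection lag are guesses, the human half-life is unknown, and the sponsor still set 6 months as its own precaution.

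The yield is limited. The last scheduled HCG test is at the end-of-treatment visit (section 4.3.4), the 8-weekly follow-up visits list no pregnancy enquiry (section 4.3.5), and follow-up stops at data cutoff. Most extra reports would be volunteered by subjects.

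A reader might infer three stronger points that the documents do not support:

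- That nothing about a late pregnancy would be reported. Adverse outcomes remain SAEs without a time limit.
- That 3.5 to 5 months are uncovered as a matter of fact. The text alone gives 3 months; the rest depends on the assumed lag and a literal reading of the trigger, while the two paragraph headings speak of becoming pregnant.
- That the 6-month duty rests on criterion 7 alone. Appendix III ends its main list at the last dose, but by saying that further methods may also be accepted in the next 6 months it presupposes that contraception continues.

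**Conclusion.** The point holds as a mismatch in safety reporting. Followed exactly, section 8.7 leaves pregnancies first found in months 3 to 6, and any conceived earlier but found after month 3, without a form or prospective follow-up, although contraception was required when they were conceived. The documented gap is 3 of 6 months; with an assumed detection lag of 0.5 to 2 months it is 3.5 to 5.

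The loss is mainly the pregnancy report, normal outcomes and prospective follow-up. No endpoint, dose decision or error rate is affected. The protocol does not say how many subjects will be of childbearing potential, but with 31 to 78 planned in total and advanced cancer required for entry, few such pregnancies are expected. The change is still worth making because it is cheap and the data cannot be recovered later.

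**What to change.** In both paragraphs of section 8.7, replace the 3-month detection window with one based on conception: pregnancies conceived from the start of administration to 6 months after the last dose, whenever the investigator becomes aware of them. State that reports arriving after data cutoff go by form to the sponsor or CRO, since the eCRF may no longer be open. Changing only the number from 3 to 6 would be better than the present text but would still miss pregnancies recognized late.

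As a separate minor consistency correction, let the main method list in Appendix III run to 6 months after the last dose of study drug, in line with criterion 7 and with the second list in the same appendix.

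The cost is three short wording changes and a few extra pregnancy reports, mostly self-reported and some after data cutoff. No added visits or tests are needed.

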### Female partners of male subjects become pregnant:

If the female partners of male subjects are found pregnant during the study (from the start of administration to within 3 months after the last dose), the investigator should complete Pregnancy Reporting Form within 24 hours of awareness, report to the sponsor/CRO in an expedited manner, record it in the source medical records and the eCRF. Under the permission of the study site, the pregnant partner should sign an authorization form of the use and release of pregnancy health information to allow the follow-up for the outcomes of their pregnancy (e.g., normal birth, preterm labour, spontaneous abortion, induced abortion, stillbirth, death neonatal, congenital anomaly or birth defect, etc.).

The investigator should propose advice to the subjects and their female partners and discuss the risks of continuing pregnancy and the possible effects on the fetus. The male subjects are not required to discontinue the study drug or withdraw from this study, however, their female partners should be monitored until the end of pregnancy.

# 9. Data Management

See the data management plan for detailed data management methods, e.g., collection and management procedures of trial data, system used for data collection and management, steps and tasks of data management, and quality assurance measures for data management.

#### 9.1 Completion and Transfer of Source Data and eCRF

- 1) The investigator should supervise the data collection and the responsibility implementation of all trial staff at the study site.
- 2) The investigator should ensure that all clinical trial data are obtained from clinical trial source files and trial records, and are accurate, complete, readable and timely. Source data should be attributable, legible, contemporaneous, original, accurate, complete, consistent and enduring. In case of any amendment to source data, it should be marked, rather than being covered up, and the reasons for such amendment should be recorded. In the trial, relevant medical records should be entered into the outpatient service system or the inpatient record system. When the information-based system of the clinical trial institution manages to establish the electronic medical record of clinical trials, the investigator should give preference to such system, which should be equipped with perfect permission management and audit trail, be able to date back to the record creator or modifier, and ensure the traceability of all the source data collected.
- 3) The investigator should complete and modify the eCRF in accordance with the instructions provided by the sponsor and ensure that the data in various eCRFs and other reports is accurate, complete, clear and timely. The data in the eCRF should be consistent with the source documents. If there is any inconsistency, a reasonable explanation should be made. Modification of data in the eCRF should keep the initial record clear and legible and modification trail should be kept. Reasons should be given when necessary and the modifier should sign and date.

The sponsor should have written procedures to ensure that their changes to eCRF are necessary, recorded, and approved by the investigator. The investigator should keep records of revisions and corrections.

### 9.2 Database Design

The Data Department of the CRO is responsible for data management of this study, and an electronic data capture (EDC) system is used to ensure the authenticity, integrity, privacy and traceability of the clinical study data.

The eCRF database is established by Data Department of CRO in the system in accordance with the requirements of Food Drug Administration 21 CFR Part 11. The database allows management of data traces such as system logins, data entry, modification and deletion, etc. The database will

be established according to the standards developed by the Clinical Data Interchange Standards Consortium as far as possible.

#### 9.3 Data Entry

In accordance with the corresponding SOP, the investigator or personnel authorized by the investigator entered the information to the EDC system in a timely manner after the completion of visits strictly according to principle of "input what you see". After the data are entered, any correction to eCRF will be automatically recorded in the system.

#### 9.4 Data Verification

Data manager (DM) will set logic verification program in EDC system according to the final data verification plan.

After the data are entered into EDC system, if there is any data not conforming to logic, the system verification will be initiated and trigger data queries. These inquiries have to be reviewed and responded by the investigator or the person authorized by the investigator. If updated data makes logic verification no longer valid, data inquiry will be closed immediately; if the study site confirms data and provides response, DM should review the response. If the reason is acceptable, the data inquiry will be closed; if data problem is not resolved, DM can continue adding data inquiry to communicate with the study site until final resolution.

Subject data listings/reports will be generated through programming to support manual data verification throughout the study. If data has to be clarified/verified/confirmed by the investigator, manual inquiry can be added in EDC system. DM should ensure that all queries are resolved before database lock and the investigator completes electronic signature in EDC system to ensure the integrity and accuracy of subject data in the EDC system.

#### 9.5 Medical Coding

DM in Data Management of CRO are responsible for medical coding of this study. Coding contents include past medical history, AEs, and concomitant medications.

Prior medical history and AEs will be coded using the Medical Dictionary for Regulatory Activities (MedDRA) (current or updated version). Previous medications and concurrent/concomitant medications will be coded according to the WHO Drug Dictionaries (current version or updated version).

During the coding process, if the data cannot be coded due to inappropriate, inaccurate, ambiguous medical terms, DM will ask the investigator to check and confirm it in the manner of data queries.

Before database lock, DM will send medical coding report to the sponsor for review.

